10.4.5 Baseline Descriptive Statistics

All data regarding subject demographics and baseline characteristics will be summarized on the ITT, overall and by treatment group, by means of summary descriptive statistics.

A complete description of subject disposition will be provided, overall and by treatment group specifying the number of randomized subjects, discontinued subjects, and the reason for the discontinuation.

The analysis populations will be described and the reasons for excluding the subject from any analysis set will be provided with the number of protocol violators per each criterion.

Medical history data will be presented by MedDRA SOC and PT.

10.4.6 Treatments (Study Treatment, Concomitant Therapies)

The Safety set will be used for the following analyses.

Investigational Treatment

Duration of study treatment, cumulative dose, average daily dose, actual dose intensity, and relative dose intensity of each of the components of study treatment will be summarized by treatment arm and for every 28-day cycle. The number of subject with dose changes/interruptions will be presented by treatment group, along with the reasons for the dose change/interruptions.

Concomitant Treatments

Concomitant medications or procedures and significant non-drug therapies taken concurrently with the study treatment will be listed and summarized by World Health Organization (WHO) Anatomical Therapeutic Chemical (ATC) Class, PT, and treatment arm. These summaries will include medications starting on or after the start of study treatment (defined as C1D1) or medications starting prior to the start of study treatment and continuing after the start of study treatment. Any prior medication or significant non-drug therapy starting and ending prior to the start of study treatment will be listed.

For the analyses of transfusions, only transfusions received after start of study treatment and up to 30 days after last dose will be considered. The number of subjects with transfusions and number of transfusions per subject will be analyzed.

10.4.7 Planned Interim Analyses

An interim analysis will be performed by the IDMC, consisting of 2 clinicians and 1 statistician who are independent experts not otherwise participating in the study, when 113 PFS events arising from both DaraPomDex and PomDex arms, which is 60% of the total planned events, have been accumulated. The purpose of this interim analysis is to evaluate cumulative interim safety and efficacy data. The significance level at this interim analysis to establish the superiority of DaraPomDex over PomDex with regard to PFS will be determined based on the observed number of PFS events at the interim analysis, using the O'Brien-Fleming boundaries as implemented by the Lan-DeMets alpha spending method (ie, 0.0038 if observing exactly 113 events). If the stopping boundary is crossed at the interim analysis, the IDMC may recommend early stopping for superiority, as well as cross-over of subjects who have disease progression on PomDex alone, based on their unblinded review of the efficacy and safety data.

10.4.8 Additional Sub-group Analyses

Additional sub-group analyses will be detailed in the SAP.

10.4.9 Multiple Comparison/Multiplicity

Unless stated otherwise, one-sided alpha level 0.025 will be considered. Strong control of family-wise Type I error rate will be controlled at a one-sided significance level of 0.025 for the following major secondary endpoints: OS, ORR, VGPR or better rate, CR or better rate, and MRD negativity rate. A hierarchical testing procedure will be used. Details about this procedure will be specified in the SAP for this study.

10.4.10 Exploratory Analyses

Additional exploratory analyses will be detailed in the SAP.

10.5 SAMPLE SIZE

Based on the primary endpoint PFS, at a one-sided significance level of 0.025, assuming exponential survival distribution with a HR of 0.621, a total of 280 evaluable subjects (140 per arm) are required to observe 188 events to test the hypothesis with 90% power. Assuming a 7% rate for permanent early censoring before the study cutoff, approximately 302 subjects will need to be randomized (151 per arm).

The primary analysis of PFS will occur after approximately 188 PFS events have been observed. The actual timing of the analysis will depend on the event rates in both control and treatment arms and will be monitored during the study. Long-term survival follow-up will continue until approximately 166 deaths have been observed. Therefore, this study will achieve approximately 70% power to detect a 34% reduction in the risk of death (HR=0.66) with a log-rank test (one-sided alpha=0.025).

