Drug administration and follow-up visits will occur more frequently for early cycles (eg, weekly or bi-weekly) (see [Table 7.3](#)). Disease evaluations will occur every cycle and consist mainly of measurements of myeloma proteins. Other parameters may include bone marrow examinations, skeletal surveys, assessment of extramedullary plasmacytomas, and measurements of serum calcium corrected for albumin. Patient reported outcome measures will be administered on Day 1 of each treatment cycle, prior to receiving treatment or any other assessment. The schedule of assessments will be adjusted for subjects remaining on study after the positive primary analysis and is detailed in [Section 7.2.4](#). A schedule of assessments is provided in [Appendix 12](#) (and detailed in [Table 7.3](#)) for subjects continuing on study treatment after the CCO for the final OS analysis.

Assessment of myeloma response and disease progression will be conducted in accordance with the modified IMWG response criteria.

Survival status, subsequent anti-myeloma treatment data, and PRO measures will continue to be collected post-treatment.

The primary analysis of PFS will occur after 188 PFS events have been observed. Long-term survival follow-up and data collection will continue until approximately 166 deaths have been observed or 5 years after the last subject is randomized, whichever occurs earlier. Subjects benefiting from the study treatment can continue to receive study treatment after the CCO for the final OS analysis. For these subjects, study treatment will be available through continued access within the current study until it is available through another source such as commercial availability with reimbursement, continued access through a long-term extension study, a patient access program, or after the last subject transitions into the long-term extension phase of the study up to 30 September 2024, whichever occurs first.

Figure 4.1: Study Design

*The schedule of assessments will be adjusted for subjects remaining on the study after the positive primary analysis and is detailed in *Section 7.2.4*. A schedule of assessments is provided in *Appendix 12* (and detailed in *Table 7.3*) for subjects continuing on study treatment after the CCO for the final OS analysis.

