10.6 MEASURES TO MINIMIZE BIAS

10.6.1 Enrollment/ Randomization/ Masking Procedures

Subject Numbering

Each subject is identified in the study by a Subject Number (Subject No.), that is assigned when the subject is first enrolled for screening and is retained as the primary identifier for the subject throughout his/her entire participation in the study. The investigator or designated staff will contact the Interactive Web Response System (IWRS) and provide the requested information for the subject to register them into the system. Once assigned, the Subject No. must not be reused for any other subject and the Subject No. for that individual must not be changed. If the subject fails to be randomized for any reason, then the reason will be entered into the Screening Disposition page.

Treatment Assignment/Randomization

Subjects will be assigned to 1 of the treatments (ie, DaraPomDex vs. PomDex) in a 1:1 ratio stratified by number of lines of prior therapy (1 vs. 2-3 vs. ≥ 4) and ISS stage (1, 2, 3). Subjects who already began treatment with daratumumab for IV infusion (Dara IV) prior to Amendment 1 approval will be offered the option to switch to SC dosing through study end, and they will be counted toward a total of 302 subjects.

The randomization numbers will be generated using procedures that ensure that treatment assignment is unbiased. A subject randomization list will be produced by the IWRS provider using a validated system that automates the random assignment of subject numbers to randomization numbers. These randomization numbers are linked to the different treatment arms, which in turn are linked to medication numbers.

Prior to dosing, all subject who fulfill all inclusion/exclusion criteria will be randomized via IWRS to 1 of the treatment arms. The investigator or his/her delegate will log on to the IWRS and confirm that the subject fulfills all the inclusion/exclusion criteria. The IWRS will assign a randomization number to the subject, which will be used to link the subject to a treatment arm and will specify a unique medication number for the first package of study treatment to be dispensed to the subject.

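### The stated overall survival power does not follow from its own inputs: 166 deaths at HR 0.66 give about 76% power, and 70% power at 166 deaths corresponds to HR 0.68

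*Combined protocol and SAP*

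**What the plan says.** Section 10.5 of the protocol gives every element of the OS calculation in two adjoining sentences. The event count comes first: "Long-term survival follow-up will continue until approximately 166 deaths have been observed". The power statement is then drawn from it: "Therefore, this study will achieve approximately 70% power to detect a 34% reduction in the risk of death (HR=0.66) with a log-rank test". The significance level is given in the same sentence: "with a log-rank test (one-sided alpha=0.025". Section 10.6.1 specifies randomisation "in a 1:1 ratio stratified by number of lines of prior therapy" and ISS stage.

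Section 4.1, and the Study Duration part of the Protocol Summary, describe a different end of follow-up: "until approximately 166 deaths have been observed or 5 years after the last subject is randomized, whichever occurs earlier". Section 7.2.4 also names the 5-year alternative. The power statement in Section 10.5 does not mention it.

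Nothing in Section 10.5 ties the OS figure to a reduced alpha, an OS interim look, an allowance for crossover or non-proportional hazards. The only interim efficacy test described is for PFS, at 113 events (Section 10.4.7).

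**The concern.** For a log-rank test, the number of deaths, the hazard ratio, the one-sided alpha and the allocation ratio fix the power, to a close approximation. All four are stated, and they do not give 70%. At least one of the printed figures is therefore wrong.

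OS is one of the major secondary endpoints under family-wise error control in Section 10.4.9. The 166 deaths also mark the final OS cutoff and the end of eCRF data collection (Section 6.1.6). A reader who wants to know what survival effect this design could reasonably detect will look to this sentence, particularly if the OS result is not significant. As printed, it describes an effect for which the design does not have 70% power.

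**Working it through.** **Inputs.** Deaths D = 166, HR = 0.66, one-sided alpha = 0.025 (z = 1.960), stated power 70% (z = 0.5244), all from Section 10.5. Allocation 1:1, from Section 10.6.1.

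**Step 1. Does the standard formula reproduce the PFS sizing in the same section?** Schoenfeld, 1:1: power = Φ(√D/2 × |ln HR| − 1.960).

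- PFS, 188 events, HR 0.621: √188/2 × 0.4764 − 1.960 = 3.266 − 1.960 = 1.306, so power is 90.4%, against 90% stated. Freedman's formula gives 89.4%.
- Early censoring: 280/(1 − 0.07) = 301.1, which is 302 with equal arms, as stated.

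The PFS figures reproduce.

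**Step 2. The OS power as stated.**

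- Schoenfeld: √166/2 × |ln 0.66| − 1.960 = 6.442 × 0.4155 − 1.960 = 0.717, so power is **76.3%**.
- Freedman: √166 × (1 − 0.66)/(1 + 0.66) − 1.960 = 12.884 × 0.2048 − 1.960 = 0.679, so power is **75.1%**.

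The stated 70% is not reproduced.

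**Step 3. What would be consistent with 70%?** Deaths required = 4 × (1.960 + 0.5244)² / (ln HR)² = 24.69 / (ln HR)².

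| Held fixed | Solved for | Result |
|---|---|---|
| HR 0.66, 70% power | deaths | 24.69/0.1727 = 143.0 (Freedman 148) |
| HR 0.68, 70% power | deaths | 24.69/0.1487 = 165.99 |
| 166 deaths, 70% power | HR | exp(−2 × 2.4844/12.884) = 0.680 (Freedman 0.677) |
| 166 deaths, HR 0.66, 70% power | one-sided alpha | 0.0157 |

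**Step 4. Could an unstated assumption close the gap?** Each line uses 166 deaths and HR 0.66 unless noted. The varied inputs are assumptions, not protocol figures.

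| Variant | Power |
|---|---|
| Deaths split unevenly between arms, 40:60 to 47:53 | 74.6% to 76.2% |
| HR at its rounding limit, 0.665 | 74.8% |
| Final OS level lowered to 0.0245 or 0.0238 by an OS interim look | 76.1% or 75.7% |
| 7% fewer deaths (154.4) | 73.3% |
| 0.025 read as two-sided | 66.8% |
| One-sided 0.05 | 84.9% |

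Simulated log-rank tests agree with the formulas. They used 302 subjects, a cut at 166 deaths, an assumed 24-month uniform accrual and 2,000 runs per setting. With assumed control median OS of 12.7, 24 and 30 months, power at HR 0.66 was 75.8%, 76.4% and 76.6%. At HR 0.68 with a 24-month median it was 69.6%. None of the HR 0.66 variants comes within 2 points of 70%.

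**Step 5. The 5-year limit.** If follow-up ended with fewer than 166 deaths, power at HR 0.66 would fall. At 143 deaths it would be 70%. At 120 deaths, √120/2 × 0.4155 − 1.960 = 0.316, or about 62%. These counts are illustrations. The protocol gives no control-arm OS or accrual assumption from which to judge whether the limit would be reached first.

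**The case against.** The arithmetic is hard to defend, so the case on the other side is about weight and remedy.

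- **The error may be harmless.** If HR 0.66 was intended, power is understated and the design is better than described. PFS drives the sample size, and correcting the OS sentence changes no alpha, test or event trigger. This stands, and it lowers the seriousness of the point.
- **A non-significant OS result would be read from its confidence interval.** Section 10.4.3 has OS analysed like PFS, with a hazard ratio and 95% interval. This stands in part: the interval matters more than planned power, but a planning statement should still be correct.
- **The wrong figure is not identified.** The HR of 0.66 and the 34% reduction agree with each other, so a misprint would have to affect both, and the death count could in principle be the faulty figure. That HR 0.68 returns 165.99 deaths is suggestive but remains an inference. However, 166 deaths is the operating trigger repeated across the protocol, so restating the HR or the power are the corrections that leave the design as it is.
- **The word approximately covers the difference.** It does not comfortably stretch over 5 to 6 points when the PFS figures in the same section reproduce to within half a point by Schoenfeld.
- **The 5-year limit is disclosed elsewhere and is a separate matter.** It is disclosed, but Section 10.5 derives the power from reaching 166 deaths without that condition.

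**Conclusion.** The point holds. At 166 deaths, HR 0.66, one-sided 0.025 and 1:1 allocation, power is about 76% (75.1% to 76.3% by the two standard formulas), not 70%. Seventy percent power at 166 deaths belongs to HR 0.68. The misstatement is about 6 percentage points of power, or 0.02 on the hazard ratio scale. This rests on proportional hazards and a single final OS test at the stated level, and the protocol gives nothing that departs from either for this figure. The documents do not show which printed figure is wrong. The primary analysis and Type I error are unaffected, so this is a clear error in a secondary planning statement rather than a flaw in the design.

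**What to change.** The sponsor should go back to the original OS calculation, establish which figure was intended, and restate the sentence in Section 10.5 as one consistent set:

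- 166 deaths give approximately 70% power to detect a 32% reduction in the risk of death (HR 0.68), one-sided 0.025; or
- 166 deaths give approximately 76% power to detect a 34% reduction (HR 0.66), one-sided 0.025.

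In either case, add that the figure applies only if 166 deaths are observed before the 5-year limit in Section 4.1. If a separate SAP repeats the OS power, make the same correction there; no SAP sample-size text is in the document reviewed. The cost is one sentence, with no change to patients, events or timelines.

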10.6 MEASURES TO MINIMIZE BIAS

10.6.1 Enrollment/ Randomization/ Masking Procedures

Subject Numbering

Each subject is identified in the study by a Subject Number (Subject No.), that is assigned when the subject is first enrolled for screening and is retained as the primary identifier for the subject throughout his/her entire participation in the study. The investigator or designated staff will contact the Interactive Web Response System (IWRS) and provide the requested information for the subject to register them into the system. Once assigned, the Subject No. must not be reused for any other subject and the Subject No. for that individual must not be changed. If the subject fails to be randomized for any reason, then the reason will be entered into the Screening Disposition page.

Treatment Assignment/Randomization

Subjects will be assigned to 1 of the treatments (ie, DaraPomDex vs. PomDex) in a 1:1 ratio stratified by number of lines of prior therapy (1 vs. 2-3 vs. ≥ 4) and ISS stage (1, 2, 3). Subjects who already began treatment with daratumumab for IV infusion (Dara IV) prior to Amendment 1 approval will be offered the option to switch to SC dosing through study end, and they will be counted toward a total of 302 subjects.

The randomization numbers will be generated using procedures that ensure that treatment assignment is unbiased. A subject randomization list will be produced by the IWRS provider using a validated system that automates the random assignment of subject numbers to randomization numbers. These randomization numbers are linked to the different treatment arms, which in turn are linked to medication numbers.

Prior to dosing, all subject who fulfill all inclusion/exclusion criteria will be randomized via IWRS to 1 of the treatment arms. The investigator or his/her delegate will log on to the IWRS and confirm that the subject fulfills all the inclusion/exclusion criteria. The IWRS will assign a randomization number to the subject, which will be used to link the subject to a treatment arm and will specify a unique medication number for the first package of study treatment to be dispensed to the subject.

10.6.2 Blinding - Unblinding

Since this is an open-label study, the treatment will be open to subject, investigator staff, and personnel performing the assessments.

11 SOURCE DOCUMENTS AND ACCESS TO SOURCE DATA/DOCUMENTS

Each participating site will maintain appropriate medical and research records for this study, in compliance with ICH E6 and regulatory and institutional requirements for the protection of confidentiality of subject. Each site will permit authorized representatives of Regulatory Agencies to examine (and when permitted by applicable law, to copy) clinical records for the purposes of quality assurance reviews, audits, and evaluation of the study safety, progress, and data validity.

Source data are all information, original records of clinical findings, observations, or other activities in a clinical study necessary for the reconstruction and evaluation of the study. Examples of these original documents and data records include, but are not limited to, hospital records, clinical and office charts, laboratory notes, memoranda, pharmacy dispensing records, recorded data from automated instruments, copies or transcriptions certified after verification as being accurate and complete, microfiches, photographic negatives, microfilm or magnetic media, x-rays, and subject files and records kept at the pharmacy, at the laboratories, and medical-technical departments involved in the clinical study.

The eCRF will not be the only record of the subject's participation in the study in order to ensure that anyone who accessed the subject's medical record would have adequate knowledge that the subject is participating in the study.

Inclusion/Exclusion Criteria Source Documentation Requirements

The minimum source documentation requirements for the Inclusion/Exclusion criteria that specify a need for documented medical history (see [Section 5.1](#) and [Section 5.2](#)) are the following:

- Referral letter from treating physician
- Complete history of medical notes at the site
- Discharge summaries

12 QUALITY ASSURANCE AND QUALITY CONTROL

Following written Standard Operating Procedures, the monitors will verify that the clinical study is conducted and data are generated, documented (recorded), and reported in compliance with the protocol, GCP, and the applicable regulatory requirements (eg, Good Laboratory Practices [GLP], Good Manufacturing Practices [GMP]).

The investigational site will provide direct access to all study-related sites, source data/documents, and reports for the purpose of monitoring and auditing by the Sponsor, and inspection by local and regulatory authorities.

13 ETHICS/PROTECTION OF HUMAN SUBJECTS

13.1 ETHICAL STANDARDS

This clinical study shall be implemented and reported in accordance with the ICH Guidelines for GCP, all applicable local regulations, and with the ethical principles laid down in the Declaration of Helsinki.

13.2 INSTITUTIONAL REVIEW BOARD (IRB)/INDEPENDENT ETHICS COMMITTEE (IEC) AND COMPETENT AUTHORITY (CA)

The protocol, ICF(s), recruitment materials, and all subject materials will be submitted to the relevant Institutional Review Board (IRB)/IEC and CA for review and approval. Approval of both the protocol and the consent form must be obtained before any subject is enrolled. Any amendment to the protocol will require review and approval by the IRB/IEC and or CA before the changes are implemented to the study. All changes to the consent form will be IRB/IEC and/or CA approved; a determination will be made regarding whether previously consented subject need to be re-consented.

13.3 INFORMED CONSENT PROCESS

13.3.1 Consent/Accent and Other Informational Documents Provided to Subject

Consent forms describing in detail the study agent, study procedures, and risks are given to the subject and written documentation of informed consent is required prior to enrollment in the study and before any study-related procedure takes place.

13.3.2 Consent Procedures and Documentation

Informed consent is a process that is initiated prior to the individual's agreeing to participate in the study and continues throughout the individual's study participation. Extensive discussion of risks and possible benefits of participation will be provided to the subjects and their families. Consent forms will be IRB/IEC-approved and the subject will be asked to read and review the document. The investigator will explain the research study to the subject and answer any questions that may arise. All subjects will receive a verbal explanation in terms suited to their comprehension of the purposes, procedures, and potential risks of the study and of their rights as research subjects. Subjects will have the opportunity to carefully review the written consent form and ask questions prior to signing. The subjects should have the opportunity to discuss the study with their surrogates or think about it prior to agreeing to participate. The subject will sign the ICF prior to any procedures being done specifically for the study. The subject may withdraw consent at any time throughout the course of the study. A copy of the ICF will be given to the subjects for their records. The rights and welfare of the subjects will be protected by emphasizing to them that the quality of their medical care will not be adversely affected if they decline to participate in this study.

